Participants. We will recruit 5-10 consecutive adult inpatients (dependent on flow within the 6-month treatment window) from the Donnelly units. Inclusion criteria will be:

1. males and females
2. age 18-65 inclusive
3. fluent in English (speaking, reading, and writing)
4. having made a suicide attempt within one week preceding admission. Admission will be defined as admission to either Harford Hospital medical floor (in cases where medical stabilization is required prior to transfer to IOL) or to IOL (in cases where medical stabilization is not required). A suicide attempt will be defined as behavior that is self-directed and deliberately results in injury or the potential for injury to oneself for which there is evidence, whether explicit or implicit, of intent to die.

Exclusion criteria will be:

1. age <18 or ≥66 years old
2. history of schizophrenia spectrum disorder
3. history of mental retardation or organic brain illness
4. current substance use disorder

5. active mania or other psychiatric or medical condition that would preclude informed consent or participation in the trial, in the investigator’s opinion
6. ECT included on patient’s inpatient treatment plan. Patients who are referred for ECT after starting the study will be withdrawn from the study.

Measures. Participants will complete a brief self-report demographic form. Diagnostic status will be measured at pre-treatment using the Diagnostic Interview for Anxiety, Mood, and Obsessive-Compulsive and Related Disorders (DIAMOND).¹⁴ Suicidal ideation and behavior will be assessed using the Columbia-Suicide Severity Rating Scale (C-SSRS).¹⁵ The C-SSRS can be scored to yield an ideation severity score (range 0-5) and a behavior severity score (0-5); suicidal behavior can also be scored dichotomously (present/absent). The C-SSRS will be administered with the timeframe for the “past week” at admission (i.e., pretreatment), and “since admission” at posttreatment, and “past week” at follow-up assessments. Depressive symptoms will be measured using the Structured Interview Guidelines for the Hamilton Rating Scale for Depression (SIGH-D),¹⁶ a well-validated clinician-rated interview for depression. Treatment acceptability will be measured using the Client Satisfaction Questionnaire (CSQ),¹⁷ an 8-item self-report measure.

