Participants will be recruited by a member of the research staff on the day following their inpatient admission or later (for example in the case of a Saturday admission). Patients who meet all of the inclusion criteria and none of the exclusion criteria and agree to participate will provide written informed consent prior to any study procedures. Informed consent will be documented using the Documentation of Informed Consent Form. For patients who are admitted to the hospital involuntarily documentation of competency to provide consent will be completed as well. Only those involuntarily committed patients who have been found competent to provide informed consent for research will be consented. Patients who decline participation will not be approached again. Patients who agree to participation will undergo the informed consent process. This process will involve providing the patient with the informed consent and HIPAA authorization forms to read. The study staff member obtaining consent will highlight the voluntary nature of the research and emphasize that the patient’s decision whether or not to participate will not impact his “usual care” treatment plan; however, patients will also be informed that the information discussed with the study clinician is shared with the inpatient treatment team, and thus may be used by them when making decisions about discharge planning. Patients will be informed that they may keep the forms to review with others if they wish to do so before signing. In addition, all questions the patient has about study participation will be answered prior to obtaining written consent.

Enrolled participants will undergo a clinical assessment by an independent evaluator (IE), who will administer the DIAMOND, C-SSRS, SIGH-D, and IAT.

Participants will receive up to 10 daily sessions of CBT (depending on length of stay), lasting 1.5 hours for the first session and 1 hour for the remaining sessions, following the manualized protocol developed in Phase 1. The CBT protocol is designed to be delivered in two phases. In phase I, the therapist conducts a detailed assessment of the

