Participants will then meet with the IE again for the C-SSRS, SIGH-D, IAT, and CSQ after the 10th session or within 24 hrs. prior to discharge, whichever comes first. After discharge, participants will have a telephone interview at 1 month, 2 month, and 3 month follow-up. The IE will administer the C-SSRS during these calls. Chart review (via Epic) will also be completed on study eligible participants (whether or not recruited). Data retrieved at 1, 2, and 3-month post-discharge will include readmission rates to the IOL or ED. Whether suicide attempt preceded admission will also be recorded. Demographic and clinical information will also be collected from the medical record (age when < or = 89, sex, race/ethnicity, diagnoses, medication, length of stay, suicide method) to compare study eligible participants who were versus were not recruited to determine if the groups were matched on these variables. At least three telephone calls will be made to try to reach a participant to complete the follow-up assessments. If a participant is unable to be reached by phone for the follow-up assessment after three tries then a letter will be sent to the participant asking them to contact the IE to inform her whether or not they wish to continue in the study. If a participant fails to contact the IE within 1 week of the study team sending the letter then a second letter will be sent again requesting that the participant contact the IE to let her know whether or not they wish to continue in the study along with a date by which the participant should contact the IE. If the participant does not contact the IE by the date stated in the letter they will be withdrawn from the study.

Adverse Event reporting.

Any severe adverse events (SAEs) that occur will be reported to the HHC IRB in a timely fashion, according to policy 901. Unexpected Severe AE’s – those rated 3-5 – will be reported within 7 calendar days of learning of the event.

Analytic Plan. It is noted that this is an initial test of feasibility and is therefore not powered for statistical significance. Though we will conduct significance tests, of greater importance are the following outcomes (all analyses will be intent-to-treat):

1. Mean CSQ scores at post-treatment, indicating acceptability of treatment.
2. Percent attrition rate, indicating acceptability of treatment.
3. Mean treatment fidelity rating, indicating our capacity to administer the treatment as described.

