4. Effect size (Hedges’s *g*) of IAT D scores from pre- to post-treatment

5. Effect size (Hedges’s *g*) of C-SSRS ideation severity score from pre-treatment through follow-up
6. Effect size (Hedges’s *g*) of C-SSRS behavior severity score from pre-treatment through follow-up
7. Effect size (Hedges’s *g*) of SIGH-D score from pre-treatment through follow-up
8. Effect size (Hedge’s *g*) comparing study enrolled versus study eligible (but not recruited) participants on readmission over the follow-up.

Future Plans. The proposed study will yield feasibility and initial efficacy data that will be used to inform a grant proposal to the American Foundation for Suicide Prevention. That proposal will fund a randomized controlled trial of CBT vs. treatment as usual. Concurrently, we will develop an in-house program to train other staff in the protocol, and will submit a second grant to investigate the efficacy of the training program as well as the efficacy of CBT by those clinicians (benchmarking analysis).

Budget and Budget Justification

[name]. (Principal Investigator, 5% time, no salary requested): [name] will be responsible for overseeing all aspects of the proposed study. He will participate in weekly supervision with the therapist and with consultant [name]. [name] will conduct the outcome analyses and will bear responsibility for publishing the results of the study. [name] will donate his time to the study.

[name]. (Consultant): [name] is a leading expert in CBT for suicide prevention, the author of the treatment protocol used in the proposed study, and was principal investigator on an RCT of that protocol. His involvement is critical for ensuring adequate application of the treatment. [name] will provide a 2-day training for the clinical staff (\$11,000 for his fees plus travel expenses). Following that training, he will participate via videoconference in weekly group supervision meetings during the treatment phase of the study (\$200 x 16 meetings = \$3200).

[name]. (Project Manager, 10% time and salary): [name] will supervise the research assistant and coordinate the day-to-day operations of the study. She will participate in the weekly supervision meetings. She will also listen to audio recordings of at least 10% of all sessions to rate treatment fidelity.

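### Outcome 6's pre-to-follow-up g for suicidal behavior mainly reflects the entry criterion, so it cannot be read as evidence of efficacy

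*Combined protocol and SAP*

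**What the plan says.** All references are to the combined protocol and SAP.

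- **Analytic Plan, outcome 6:** Hedges's g "of C-SSRS behavior severity score from pre-treatment through follow-up". The standardiser and the follow-up time point are not specified. The section says that the study is not powered, that significance tests will be run, and that the listed outcomes matter more than those tests.
- **Participants, inclusion criterion 4:** "having made a suicide attempt within one week preceding admission".
- **Measures:** the C-SSRS behavior score runs from 0 to 5 and has a present/absent version. The timeframe is the past week at pre-treatment, "and “since admission” at posttreatment, and “past week” at follow-up assessments".
- **Procedures, recruitment:** "Participants will be recruited by a member of the research staff on the day following their inpatient admission or later".
- **Procedures, follow-up:** telephone C-SSRS at 1, 2 and 3 months. The chart review covers eligible patients whether or not recruited, and "Whether suicide attempt preceded admission will also be recorded".
- **Analytic Plan, outcome 8:** an effect size "comparing study enrolled versus study eligible (but not recruited) participants on readmission over the follow-up". No other between-group effect size is planned.
- **Future Plans:** the intended use of the results is stated as follows: "The proposed study will yield feasibility and initial efficacy data that will be used to inform a grant proposal". The grant is for a randomized trial.

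**The concern.** Patients are selected because the event that the outcome measures has just happened, and the baseline window is placed where that event is likely to be counted. No attempt is required in any later window, so the mean score must tend to fall. With one group, nothing in outcome 6 separates that fall from an effect of CBT, and the plan says nothing about selection at entry or regression to the mean.

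Other pre-post outcomes also lack a control, but only outcome 6 scores the very behavior that entry requires. What is at stake is the use of the result: pilot efficacy data are a stated aim, and the efficacy data are meant to support a grant proposal. A selection artefact could be reported there as a treatment effect.

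**Working it through.** The plan gives no expected g, power or event rate for outcome 6, so there is no figure to reproduce. The check asks what g would look like if treatment did nothing.

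**Inputs from the documents:** n = 5 to 10; score 0-5; past-week window at baseline and follow-up; hazard ratio 0.38 from the outpatient trial cited under Method. **Assumptions:** the score given to an attempt, the re-attempt rate, and the share of baseline interviews that capture the entry attempt.

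**Formula.** g = J × mean fall / SD, with J = 1 − 3/(4df − 1). For the SD of change, df = n − 1; for the pooled SD, df = 2n − 2. Results are given as SD of change / pooled SD.

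**Worked case.** n = 10, all baselines 5, one re-attempter scored 5 again, nine at 0.
- Mean fall = 4.5; SD of change = 1.581; J = 1 − 3/35 = 0.914; g = 0.914 × 4.5/1.581 = 2.60.
- Pooled SD = √((0 + 2.5)/2) = 1.118; J = 1 − 3/71 = 0.958; g = 0.958 × 4.5/1.118 = 3.85.
- The common baseline value cancels, so 3 or 4 in place of 5 gives the same g.

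**Scenarios**

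| Scenario | n | Re-attempts recorded | g |
|---|---|---|---|
| A: equal baselines; re-attempters repeat their score | 10 | 0 | undefined (SD = 0) |
| A | 10 | 1 | 2.60 / 3.85 |
| A | 10 | 3 | 1.32 / 1.96 |
| A | 5 | 1 | 1.43 / 2.29 |
| A | 5 | 2 | 0.88 / 1.40 |
| C: baselines 3, re-attempts scored 5 | 10 | 1 | 1.45 / 2.14 |
| C | 10 | 3 | 0.57 / 0.84 |
| C | 5 | 1 | 0.72 / 1.14 |
| C | 5 | 2 | 0.29 / 0.47 |
| D: late interview, 3 of 10 baselines at 0, the rest equal | 10 | 0 | 1.32 / 1.96 |
| D | 10 | 1 | 0.78 to 1.06 / 1.41 |

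**Selection alone, without the short recall window.** Suppose that the 3-month call recalled all 91 days, all 10 patients were reached and treatment had no effect. With re-attempts binomial(10, rate), the chance that g (SD of change) is at least 0.8 or undefined at re-attempt rates of 10%, 20% and 30% is:
- A: >99%, 99% and 95%.
- C: 93%, 68% and 38%.

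**How much of the fall is selection.** Treat the score as attempt or no attempt in the window. Let q be the share of baselines that capture the entry attempt, p the weekly risk without CBT, and p′ = 1 − (1 − p)^0.38 the risk with it. The share of the fall that occurs without treatment is (q − p)/(q − p′).
- p = 0.5%, q = 100%: p′ = 0.19%; 0.995/0.9981 = 99.7%.
- p = 20%, q = 100%: p′ = 8.13%; 0.80/0.9187 = 87%.
- p = 20%, q = 60%: 0.40/0.5187 = 77%.

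With q = 100%, the share drops below half only at a weekly risk of about 68% or more.

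**Can g tell the two cases apart?** The table gives median pooled-SD g over simulated trials in which g is defined (n = 10, q = 80%, attempts scored 5, otherwise 0).

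| Weekly risk without CBT | 1% | 5% | 10% | 20% |
|---|---|---|---|---|
| No effect | 2.57 | 1.96 | 1.80 | 1.41 |
| Hazard ratio 0.38 | 2.57 | 2.57 | 2.42 | 1.96 |

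**Secondary point: coverage.** Three past-week calls cover 21 of about 91 days (23%). If three patients each re-attempt once on a random day and all are reached, the calls miss all three with probability (1 − 0.231)³ = 46%.

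**The case against.** The strongest reply is that this is a small feasibility study that disclaims power, ties no hypothesis or go/no-go rule to outcome 6, and names as its next step a randomized trial that would supply the missing control. That limits the consequence, and it stands. It does not answer the point: low power concerns imprecision, whereas this is bias.

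A second reply is that the size depends on the scenario. This is true. Defined values in the table run from 0.29 to 3.85, an undefined g needs zero variance, and the split between selection and treatment borrows a hazard ratio from outpatients. The direction follows from the documents; the word mainly rests on the assumed ranges, across all of which it holds.

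Third, a late baseline interview may miss the entry attempt in some patients. Scenario D shows that this lowers g but does not remove the artefact.

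Fourth, g could be kept with a caveat. But a g that is inflated or undefined under no effect adds nothing to counts by window.

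Finally, recall coverage is a separate measurement limit. Follow-up uses the same past-week window as baseline, so the windows do not create the fall. Only the post-treatment window differs.

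**Conclusion.** The concern holds and should be fixed. Because entry requires a recent attempt, the baseline window is the past week and there is no comparator, outcome 6 is expected to show a fall from an inert treatment, and its g can be large or undefined. At weekly risks of 0.5% to 20% and baseline capture of 60% to 100%, 77% to 99.7% of the fall expected under a hazard ratio of 0.38 would occur anyway. Those risks, the capture rate, the scoring of attempts and the transfer of that hazard ratio to inpatients are assumptions. Confidence is high on direction and lower on exact size. Outcome 6 is one of eight and no decision threshold rests on it.

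**What to change.** In outcome 6, replace the pre-post g and its significance test with the number and percent of participants with any suicidal behavior, using the present/absent score already described in Measures, with an exact 95% confidence interval.

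- Report it separately for each window: since admission at post-treatment, and past week at 1, 2 and 3 months. Give the numbers interviewed and missing for each.
- List severity scores descriptively if wanted.
- Report alongside the attempts preceding IOL or ED readmission from the chart review, taking the admission in that sentence of Procedures to mean readmission.
- State that change from baseline in behavior is not evidence of efficacy, and that past-week counts do not cover the whole follow-up.
- Optional: report a cumulative 3-month proportion, but only if the follow-up behavior items are also asked for the time since last contact.

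**Cost.** The counts by window need only new Analytic Plan wording and use data already planned. The optional proportion needs a small change to the follow-up C-SSRS timeframe in Measures and slightly longer calls. The result will look less favourable and be imprecise: 0/10 gives 0 to 31% (1 − 0.025^(1/10) = 0.308) and 0/5 gives 0 to 52% (1 − 0.025^(1/5) = 0.522). Without the optional change, about 77% of follow-up days remain unscored by interview.

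### Follow-up suicidal behavior in outcome 6 rests only on three past-week telephone interviews, and the attempt flag already planned in the chart review is used in no listed outcome

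*Combined protocol and SAP*

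**What the plan says.** - **Outcome.** Analytic Plan, outcome 6, is the Hedges's g "of C-SSRS behavior severity score from pre-treatment through follow-up". Under Measures, the behavior score runs from 0 to 5 and may also be reduced to present or absent.
- **Source after discharge.** "After discharge, participants will have a telephone interview at 1 month, 2 month, and 3 month follow-up", and the independent evaluator gives the C-SSRS in those calls. Measures sets the recall period at follow-up to the past week.
- **Non-contact.** "If a participant is unable to be reached by phone for the follow-up assessment after three tries then a letter will be sent". A second letter follows, and a participant who does not answer by the date it gives is withdrawn.
- **Chart review.** The same follow-up paragraph plans an Epic review of all study-eligible patients, enrolled ones included. It retrieves readmissions to the IOL or ED at 1, 2 and 3 months, and adds: "Whether suicide attempt preceded admission will also be recorded".
- **Use of the chart data.** Among the eight listed outcomes, only outcome 8 draws on follow-up chart data, and it concerns readmission. None uses the attempt flag.
- **Analysis set and size.** "all analyses will be intent-to-treat", with no rule for a missing C-SSRS. Under Participants: "We will recruit 5-10 consecutive adult inpatients".

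**The concern.** The plan's only listed outcome on suicidal behavior depends, after discharge, on a completed call and on the week before that call. The study will also hold a second source, the Epic attempt flag, which does not depend on reaching the patient or on a one-week recall. Outcome 6 as written does not draw on it.

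The loss is unlikely to be neutral. A patient back in hospital after an attempt may well be harder to reach, and non-contact can end in withdrawal, which removes later calls too. The intent-to-treat statement does not settle this, because it keeps the patient in the analysis set without saying what value the patient receives.

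The stakes are modest but real. The Analytic Plan ranks these outcomes above its significance tests, and Future Plans says that the efficacy data will inform a proposal for a randomized trial. Entry requires a recent attempt, and the Rationale itself stresses the risk in the 90 days after hospitalization.

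**Working it through.** The documents give no power, alpha or expected event rate, so there is no planned figure to reproduce.

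**1. Time covered by the interviews.** Three calls of 7 days each give 3 × 7 = 21 days. Three months is 84 to 91 days, so coverage is 21/84 = 25% to 21/91 = 23%. A reached patient whose attempt fell in another week can be scored as having no behavior at all three calls.

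**2. Weight of one patient.** Suppose that one enrolled patient re-attempts, is readmitted and is never reached.

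| Enrolled | Attempt counted from chart | Telephone data alone, complete cases |
|---|---|---|
| 10 | 1/10 = 10% | 0/9 = 0% |
| 5 | 1/5 = 20% | 0/4 = 0% |

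Complete-case analysis is an assumption here. If a post-treatment score of 0 were carried forward instead, the result would be 0/10 or 0/5, and the attempt would still be missing.

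**3. How likely the situation is.** P(at least one re-attempt) = 1 − (1 − p)^n. The documents give no p, so a range is shown.

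| Assumed 3-month risk p | n = 5 | n = 10 |
|---|---|---|
| 5% | 0.23 | 0.40 |
| 10% | 0.41 | 0.65 |
| 20% | 0.67 | 0.89 |

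This is the chance that a re-attempt occurs. The chance that it is then missed cannot be derived from the documents.

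**4. Effect on the scale of outcome 6.** The scores are assumed: 4-5 at baseline, 0-1 at follow-up, and 5 for the re-attempter at both times. I used g = (mean pre − mean post)/s × (1 − 3/(4df − 1)), where s² is the average of the two variances and df = 2(n − 1).

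- n = 10, attempt counted: means 4.6 and 0.7, variances 0.267 and 2.456, s = 1.167. Then g = 3.9/1.167 × (1 − 3/71) = 3.2.
- Same sample, patient dropped (n = 9): difference 4.333, s = 0.486. Then g = 4.333/0.486 × (1 − 3/63) = 8.5.
- Same sample, score of 0 carried forward: g = 8.9.
- n = 5: g = 1.9 with the attempt counted, 6.8 with the patient dropped, 7.9 with 0 carried forward.

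The sizes of g depend on the invented scores and are not forecasts. In these examples, losing the attempt raises both the mean change and g.

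**The case against.** **Effort to limit loss.** There are three separate calls, at least three tries to reach the patient, two letters, and $50 per completed interview. The research assistant tracks inpatient admissions, so a readmission to the IOL may be noticed. This lowers the chance of loss, but leaves no rule for when it happens and does not touch the recall window.

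**The patient is not invisible.** The readmission counts in outcome 8, and withdrawal would plausibly count as attrition in outcome 2. The eight outcomes are not stated to be the only results, so the flag may be reported anyway. This stands, but neither outcome shows that an attempt occurred.

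**Which admission does the flag concern?** The sentence does not say. It follows the sentence on readmissions, and inclusion criterion 4 already requires an attempt before the index admission, so the flag is informative only for readmissions.

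**Small feasibility study.** The plan says that "this is an initial test of feasibility and is therefore not powered for statistical significance". That is a fair limit on the stakes, but this point asks for no power.

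**Stronger readings.** A reader might infer that the plan necessarily understates suicidal behavior. The documents do not support that, because the direction of bias from missed calls depends on re-attempters being harder to reach, which is not documented. A reader might also attach a figure. If 20% show behavior, and 50% of these and 90% of the others respond, responders show 0.2 × 0.5/(0.2 × 0.5 + 0.8 × 0.9) = 0.10/0.82 = 12.2%. The response rates are invented, and the sum assumes that each interview detects all behavior, contrary to the past-week window. With full response and one event at a random time, that window alone would give 20% × 21/90 = 4.7%. Neither figure is an estimate for this trial.

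**Conclusion.** The point holds as a gap in the listed analyses. Followed as written, outcome 6 can omit a re-attempt that the chart review has recorded, through non-contact or because the attempt fell in the 75-77% of follow-up time that no interview asks about. One unreached re-attempter is 10% of the sample at n = 10 and 20% at n = 5. The coverage figure follows from the protocol's own schedule. The 0/9 and 0/4 results rest on complete-case analysis, and favourable bias from missed calls rests on outcome-related non-response; the plan states neither.

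A reader might infer that merging the chart would make the record complete. It would not: Epic shows only attempts that led to an IOL or ED admission, and suicidal behavior other than an attempt would come from the interviews alone. The chart narrows the gap without closing it.

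**What to change.** Keep the Hedges's g for outcome 6 and add the following to the Analytic Plan:

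1. For all enrolled patients, including those withdrawn for non-contact where consent permits, report n/N with any suicidal behavior from discharge to 3 months, by C-SSRS interview or Epic-recorded attempt. Show how many were positive by each source.
2. Report the number of completed calls at 1, 2 and 3 months, and state how a missing C-SSRS score is handled under intent-to-treat.
3. Present the n/N as a minimum. State that negative past-week interviews with no Epic event do not prove absence of behavior over the 3 months.
4. Give a sensitivity range. With e patients positive and u patients who missed any call and have no recorded event, show e/N (all u counted as none) to (e + u)/N (all u counted as positive). The upper end is not a strict limit, since fully interviewed patients also have weeks that were not asked about.
5. State that the chart flag refers to the readmission.

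Both sources are already planned, so the change is to wording. The figure may look slightly less favourable. The range will be wide: each patient in u adds 1/N, which is 10 percentage points at N = 10 and 20 at N = 5.

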An Initial Feasibility Study of Brief Cognitive Behavioral Therapy for Suicidal Inpatients

Rationale. Suicide is a major public health problem: suicidal ideation affects 14% of the adult U.S. population, and as many as 5% have a lifetime history of suicide attempts.¹ Among individuals with depressive disorders, there is an 11% mortality rate from suicide.²

Although inpatient treatment provides immediate stabilization and crisis management, the risk of suicide post-discharge is substantial. Approximately one third of all suicides by individuals with mental disorders occur in the 90 days following hospitalization.³ A review of nearly 2 million adult psychiatric inpatients found that the suicide rate in the 90 days after discharge for patients diagnosed with depressive disorders was 235.1 per 100,000 person-years, markedly higher than that in the US general population (14.2 per 100,000 person-years).⁴

Cognitive behavioral therapy (CBT) has been shown to reduce both suicidal ideation and behavior.⁵⁻⁸ Though specific protocols vary, typical interventions include problem-solving training,⁹ cognitive restructuring,¹⁰ and training in emotion regulation skills.¹¹ To date, most of the existing research on CBT has been in outpatient samples, and the efficacy of inpatient CBT for suicide prevention is not clear.

Project Aims. The aims of the proposed project are to:

1. develop and implement a brief CBT for suicide prevention on the adult inpatient units;
2. conduct a brief feasibility test and collect initial pilot data on efficacy; and
3. collect preliminary data on the effects of CBT on implicit cognitive suicide associations.

Method. We selected [name] *et al.*'s¹² CBT protocol for the proposed project. This protocol was tested in a randomized controlled trial (RCT) of outpatients and resulted in a significant reduction in suicide attempts over a 24-month follow-up assessment (hazard ratio = 0.38); those receiving CBT were 60% less likely to make a suicide attempt than were those receiving treatment as usual.¹³ Of the 6 RCTs that measured suicidal behavior, this was the strongest behavioral effect documented.⁷

There will be two phases involved in this project, which are described below:

In Phase 1 of the project, we will work with [name] to modify his treatment protocol for use in an inpatient setting, and attend a two-day training in the protocol from [name].

In Phase 2 of the project, we will conduct an initial feasibility trial with 5-10 inpatients.

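### Outcomes 4-7 are uncontrolled changes during inpatient care plus CBT, but the aims and Future Plans describe them as efficacy data and effects of CBT

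*Combined protocol and SAP*

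**What the plan says.** All references are to the combined protocol and SAP.

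- **Design.** Under Method, "we will conduct an initial feasibility trial with 5-10 inpatients". Under Procedures, "Participants will receive up to 10 daily sessions of CBT (depending on length of stay". There is one treated group and no allocation.
- **Entry.** Participants, inclusion criterion 4, requires "having made a suicide attempt within one week preceding admission".
- **Concurrent care.** Procedures says that the patient's "decision whether or not to participate will not impact his “usual care” treatment plan", so usual inpatient care continues alongside CBT.
- **Outcomes.** Analytic Plan items 4-7 are Hedges's g values over time for the IAT D score, C-SSRS ideation, C-SSRS behaviour and SIGH-D. Item 5, for example, is the effect size "of C-SSRS ideation severity score from pre-treatment through follow-up".
- **Label.** Aim 2 includes pilot data on efficacy. Aim 3 concerns the effects of CBT on implicit suicide associations. Future Plans says: "The proposed study will yield feasibility and initial efficacy data that will be used to inform a grant proposal". It continues: "That proposal will fund a randomized controlled trial of CBT vs. treatment as usual".
- **Caveat.** The Analytic Plan notes that the study is a feasibility test without power for significance, says that tests will be run anyway, and gives more weight to its list of eight outcomes.

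**The concern.** An efficacy statement is a statement about what CBT adds to usual care. That is also what the proposed trial of CBT against treatment as usual would estimate. A pre-post change in a single treated group is a different quantity: it contains everything that happens to these patients between the two assessments. Here that includes an inpatient stay, which the protocol's own Rationale credits with stabilising patients in crisis, and the natural course after a suicide attempt.

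At stake is what a reader of the results, or of the grant proposal, may conclude. A sizeable g on ideation or depression would be reported under an efficacy label although it could arise with no contribution from CBT. Nothing in the plan tells the reader this.

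**Working it through.** The plan gives no expected effect, alpha or sample-size calculation for outcomes 4-7, so there is no figure to reproduce. The check is of what these outcomes can estimate.

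**1. What the change contains.** For each patient write

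change = U + B,

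where U is the change that would have occurred under usual inpatient care without CBT and B is what CBT adds. The pilot observes the mean of U + B. A randomised comparison estimates (U + B) − U = B. The pilot has one observed quantity and two unknowns.

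**2. Is U observed anywhere?** The only comparison group is the eligible patients who were not recruited. Procedures describes chart review for them: readmission, whether a suicide attempt preceded it, and demographic and clinical variables. They serve outcome 8 (readmission) and a check on whether the groups are matched. No IAT, C-SSRS or SIGH-D assessment is planned for them, so U is not observed for any of outcomes 4-7.

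**3. Is there reason to expect U to differ from zero?** Three places in the documents point that way.
- The Rationale attributes stabilisation to inpatient treatment itself.
- Entry follows a recent attempt, so patients start from an acute episode.
- The C-SSRS reference periods are "past week” at admission (i.e., pretreatment), and “since admission” at posttreatment, and “past week” at follow-up assessments". The post-treatment period is therefore time spent in hospital, which differs from the pre-admission setting whatever CBT does.

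**4. Does the power caveat cover this?** No. Low power means a wide interval around the mean of U + B. More patients narrow that interval but leave U in place. An illustration, with every input assumed: B = 0; SD 1 at both times; pre-post correlation 0.5; paired t-test at two-sided 0.05; 20,000 simulated studies per row. Here g = J × (mean pre − mean post) / √[(s²pre + s²post)/2], with J = 1 − 3/(4·df − 1) and df = 2n − 2.

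| Assumed improvement under usual care (SD) | Mean g, n = 5 | Significant, n = 5 | Mean g, n = 10 | Significant, n = 10 |
|---|---|---|---|---|
| 0 | 0.00 | 5% | 0.00 | 5% |
| 0.5 | 0.51 | 14.4% | 0.51 | 29.5% |
| 1.0 | 1.02 | 40.3% | 1.01 | 80.0% |
| 1.5 | 1.54 | 71.4% | 1.52 | 98.6% |

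As a check, the SD of the difference is √(1 + 1 − 2 × 0.5) = 1, so at 1.0 SD and n = 10 the noncentrality is 1.0 × √10 = 3.16 on 9 degrees of freedom, consistent with about 80%.

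The table does not estimate how large U is in this population. It shows that g tracks whatever U is, and that going from 5 to 10 patients leaves the mean g almost unchanged while making a significant result more likely.

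**5. Label against content.** Aim 3 has only one measure behind it, the IAT at pre- and post-treatment (outcome 4), which is an uncontrolled change. The efficacy data in aim 2 and Future Plans are outcomes 4-7, apart from the non-randomised readmission comparison in outcome 8. No section states that the change in outcomes 4-7 cannot be attributed to CBT.

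**The case against.** The plan is modest. Its title calls it an initial feasibility study, acceptability, attrition and fidelity head the list, there is no efficacy threshold or go/no-go rule, and the next step is a randomised trial against usual care. A single arm is normal for such a pilot. The Analytic Plan itself calls outcomes 4-7 only effect sizes over time; the efficacy wording is in the aims and Future Plans. All of this stands and limits the point to labelling and use. It does not remove it, because none of it tells the reader that the change is confounded with usual care.

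Selection is also on an event, not on the analysed scores: there is no entry threshold on ideation, SIGH-D or IAT. So a regression-to-the-mean calculation cannot simply be applied, and for the IAT the documents give no particular reason to expect a shift without CBT. That stands too. The point needs only that U is unobserved, which is true of all four outcomes.

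Two stronger readings are tempting and are not supported.
- *That the plan sizes the randomised trial on the pre-post g, leaving it underpowered.* Future Plans says only that the data will inform a grant proposal. That trial's endpoint, effect size and sample size are not given, and Method cites a controlled result for the source treatment (hazard ratio 0.38 for suicide attempts) that could be used instead.
- *That every baseline falls within about a week of the attempt.* The week runs to admission, which may be to a medical floor first, and recruitment is on the day after inpatient admission or later. No limit from attempt to baseline assessment is stated.

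**Conclusion.** The point holds as one of interpretation. Outcomes 4-7 estimate change during inpatient care plus CBT. They do not estimate what CBT adds, and the wording of aims 2-3 and Future Plans claims more than the design can support. The power caveat does not address this.

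The size of the bias cannot be given: it equals the change these patients would show without CBT, for which the documents have no figure. A reader might infer that usual care accounts for most or all of any observed change; the documents do not show that either. The conclusion rests only on the single arm, the continuing usual care and the absence of these measures in the non-recruited group, all of which are in the text. Feasibility outcomes 1-3 are unaffected.

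**What to change.** 1. **Analytic Plan.** Describe outcomes 4-7 as descriptive within-person change during inpatient care plus CBT, report each with a confidence interval, and add a sentence that they do not estimate an effect of CBT because usual care and natural recovery act over the same period.
2. **Project Aims 2-3 and Future Plans.** Align the wording: change in the outcome measures during the programme, instead of efficacy or effects of CBT.
3. **Future Plans.** State that the pre-post g values will not be used as the between-group effect size for the randomised trial, which should come from controlled data or a smallest worthwhile difference.

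The pilot should not be put forward as the source of the SD for that trial either. For normal data the 95% interval for an SD is the estimate multiplied by √[(n − 1)/χ²], with χ² taken at the upper and lower 2.5% points. That is about 0.69 to 1.83 times the estimate at n = 10 and 0.60 to 2.87 times at n = 5.

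The cost is a few sentences and a less favourable headline for the grant. No new arm, visit or measurement is needed.
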